9.0 Subject Disposition

The number of subjects for each of the following categories will be summarized by treatment group and overall:

- All randomized subjects
- Subjects who took at least one dose of study drug
- Subjects who completed the Treatment Period
- Subjects who discontinued from the Treatment Period
- Subjects who enrolled in the extension study
- Subjects who completed the Post-Treatment Follow-Up Period
- Subjects who prematurely discontinued from the Post-Treatment Follow-Up Period

Premature discontinuation of the study drug by primary reason and by any reason will be summarized for each treatment group and overall, with number and percentage overall and by reason for discontinuation for all subjects who received at least one dose of study drug. Subjects may have multiple reasons for prematurely discontinuing study drug, but will be counted no more than once for the total of "Any Reason."

Premature discontinuation during the Post-Treatment Follow-up Period by primary reason and by any reason will be summarized for each treatment group and overall, with number and percentage overall and by reason for discontinuation. Subjects may have multiple reasons for prematurely discontinuing during the Post-Treatment Follow-up Period, but will be counted no more than once for the total of "Any Reason."

10.0 Study Drug Exposure

Exposure to study drug will be summarized for the safety analysis set. The duration (days) of study drug treatment will be summarized with the mean, SD, median, minimum, and maximum for each treatment group and overall. The duration of treatment is defined as the difference between the dates of the first and last doses of the treatment plus 1 day. The duration (days) of study drug treatment will also be summarized by treatment group and overall with number and percentage for the following categories: 1 – 28 days, > 28 – 56 days, > 56 – 84 days, > 84 – 112 days, > 112 – 140 days, > 140 – 168 days, > 168 – 196 days, and > 196 days.

11.0 Efficacy Analysis

11.1 General Considerations

Unless otherwise stated, all statistical tests will be conducted at an alpha level of 0.05 (two-sided). A test will be deemed significant if the *P* value rounded to three decimal places is less than or equal to 0.05, unless otherwise specified. For analyzing efficacy variables, each elagolix dose group will be compared with placebo. The elagolix dose groups will not be compared against each other unless otherwise specified. The primary efficacy comparison will be between the elagolix 300 mg BID plus E2/NETA group and the placebo group. The comparison between the elagolix 300 mg BID alone group and the placebo group will be used as a reference and to examine the validity of the study design.

Unless otherwise specified, categorical data will be summarized by frequency and percentage; descriptive summaries of continuous data will display the mean, SD, median, minimum, and maximum.

For continuous variables, when the analyses of change and/or percent change from Baseline to post-baseline visit(s) are performed, the within-group change from Baseline to each relevant visit will be summarized by treatment group with the mean, SD, and 95% Confidence Intervals (CIs). The between-group differences will be summarized with the

mean, SE, 95% CIs, and *P* value when applicable. At each post-baseline visit, the Baseline mean and post-baseline visit mean will be calculated for all subjects with baseline and post-baseline value at that visit by treatment group.

Information regarding corresponding statistical methods for analyses and any additional statistical measures required for a specific variable/endpoint are provided in the relevant sections.

Unless otherwise specified, there will be no hypotheses testing for efficacy endpoints in the Post-Treatment Follow-up Period.

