8.0 Statistical Methods and Determination of Sample Size

8.1 Statistical and Analytical Plans

8.1.1 General Considerations

The SAS system will be used to perform the statistical analyses. All statistical tests will be two-sided and a significance level of 0.05 will be used unless otherwise specified. A test will be deemed statistically significant if the *P* value rounded to three decimal places is less than or equal to 0.05 unless otherwise specified. The primary safety and efficacy comparisons will be between the elagolix 300 mg BID plus E2/NETA treatment group and the placebo group. Comparisons between the elagolix 300 mg BID alone treatment group and the placebo group are provided for a reference.

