3.0 Introduction

This statistical analysis plan (SAP) describes the planned statistical analyses for elagolix (ABT-620) Study M12-815 titled "A Phase 3 Study to Evaluate the Efficacy and Safety of Elagolix in Combination with Estradiol/Norethindrone Acetate for the Management of Heavy Menstrual Bleeding Associated with Uterine Fibroids in Premenopausal Women." The analysis plan was created based on the Study Protocol M12-815 Amendment 3 dated 25 September 2017.

This analysis plan describes both the efficacy and safety analyses. The pharmacokinetic data will be analyzed separately and is not addressed in this SAP.

The SAS System 9.2 or above will be used to perform the statistical analyses. All statistical tests will be two-sided and a significance level of 0.05 will be used unless otherwise specified.

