4.4 End-of-Treatment Period Analysis

An end-of-treatment period analysis of the primary and secondary efficacy variables along with demographic and safety variables will be performed after the last subject completes the 6-Month Treatment Period of Study M12-815. This end-of-treatment period analysis will include all treatment period data from all patients randomized into the study. The data base will be versioned and any discrepant data will be clarified before the lock. Analyses will be performed by an external Independent Data Analysis Center (IDAC).

Subjects completing Study M12-815 are eligible to be enrolled in the double-blind extension study. The blinding at the subject level for the extension study will be maintained as the efficacy data analyses will only present overall treatment group results to the sponsor. The sponsor will have access to the unblinded results at the treatment group level. However, the blinded data at the subject level will not be included in the results of the demographic, efficacy, or safety endpoints provided to the sponsor. The randomization schedule for Study M12-815 will be provided to the IDAC by someone other than the project statistician, who is otherwise not involved with this study. All AbbVie study personnel will remain blinded until the blind is broken for the double-blind extension study. The end-of-treatment period analysis will only include data collected during the 6-month treatment period of the study and will not include data collected during the Post-Treatment Follow-up Period.

Since this end-of-treatment period analysis is the only and final analysis of the primary and ranked secondary endpoints of Study M12-815, no adjustment of alpha-level is necessary.

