11.4 Handling of Multiplicity

The primary comparison for all analyses will be made between elagolix 300 mg BID in combination with E2/NETA and placebo. The elagolix 300 mg BID alone group serves as a reference arm.

Therefore, no adjustment of the type I error rate (alpha) for primary analysis of the primary endpoint is needed. Ranked secondary endpoints will follow a fixed-sequence testing procedure.¹¹

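### Minor: the plan states a two-sided 0.05 level, but its rounding rule also passes P values between 0.0500 and 0.0505

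*SAP*

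**What the plan says.** The significance level appears in three places. SAP Section 3.0 says "All statistical tests will be two-sided and a significance level of 0.05 will be used unless otherwise specified", with no mention of rounding. SAP Section 11.1 repeats the two-sided 0.05 level for efficacy and, in the next sentence, declares a test significant if the P "value rounded to three decimal places is less than or equal to 0.05". Protocol Section 8.1.1 pairs the same level with the same rule: the P "value rounded to three decimal places is less than or equal to 0.05 unless otherwise specified".

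No other section gives a different threshold for the confirmatory tests. SAP Section 4.4 says "no adjustment of alpha-level is necessary" for the primary and ranked secondary endpoints because there is only one final analysis. SAP Section 11.4 says "no adjustment of the type I error rate (alpha) for primary analysis of the primary endpoint is needed", and adds "Ranked secondary endpoints will follow a fixed-sequence testing procedure" without naming a cutoff for the steps.

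SAP Section 11.1 also reports between-group differences for continuous variables with the "mean, SE, 95% CIs, and" P value, where applicable.

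**The concern.** A P value of 0.0501 or 0.0504 exceeds 0.05 but rounds to 0.050. The plan would call it significant although the level stated one sentence earlier says it is not. Compared with an unrounded 0.05 rule, the discrepancy can only help the sponsor, because it adds rejections and never removes one.

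The visible consequence would be in the ranked secondary endpoints. Four of the six in SAP Section 11.3 are continuous: change in menstrual blood loss volume to the Final Month, Month 6, Month 3 and Month 1. These are tested by ANCOVA or MMRM. If one of them gave a P value in the band, it would be declared significant and the fixed sequence would continue, while the 95% confidence interval from the same model included zero. The study's own tables would then contradict each other.

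**Working it through.** **Inputs.** Two-sided level 0.05 and the rounding rule (SAP 11.1, Protocol 8.1.1). Responder rates of 60% and 30%, with 200 on combination treatment and 100 on placebo (SAP 4.3, Protocol 8.2). Stated power is at least 90%.

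**1. The plan's power figure.** With unpooled variance, SE = √(0.6×0.4/200 + 0.3×0.7/100) = √0.0033. Under the null, pooled p = (120 + 30)/300 = 0.5 and SE₀ = √(0.25 × (1/200 + 1/100)) = √0.00375. Power = Φ[(0.30 − 1.9600×√0.00375)/√0.0033] = 0.9991. The stated minimum of 90% is met; it would need only 42 and 84 subjects (47 and 94 with continuity correction).

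**2. What the rule accepts.** Rounding to three decimals and comparing with 0.050:

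| P value | P ≤ 0.05? | Rounded | Passes the rule? |
|---|---|---|---|
| 0.05000 | yes | 0.050 | yes |
| 0.05001 | no | 0.050 | yes |
| 0.05049 | no | 0.050 | yes |
| 0.05051 | no | 0.051 | no |

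The extra rejection region is 0.0500 < P < 0.0505. (Exactly 0.0505 depends on the rounding convention and is immaterial.) If P is uniform under the null, the nominal size is 0.0505, an excess of 0.0005, or 1% in relative terms. The critical |z| falls from 1.9600 to 1.9557.

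**3. Any single test with an approximately normal statistic.** The probability of landing in the band is 0.0505 − 0.0500 = 0.0005 under the null. Over all true effects it peaks when the statistic is centred on the band: width × φ(0) = (1.95996 − 1.95570) × 0.3989 = 0.0017.

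**4. The primary test at the planning assumptions.** These are unadjusted stand-ins for the logistic regression pooled over 20 imputed datasets:

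| Method | Power at 0.05 | Power at 0.0505 | Difference |
|---|---|---|---|
| Normal, unpooled variance | 0.999448 | 0.999456 | 8.2e-6 |
| Normal, pooled variance | 0.999135 | 0.999148 | 1.3e-5 |
| Exact enumeration, pooled chi-square | 0.999033 | 0.999074 | 4.1e-5 |
| Exact enumeration, Wald log odds ratio | 0.998810 | 0.998890 | 8.0e-5 |

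The difference is the chance that the primary P value falls in the band. It is below 1 in 10,000 by every method.

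**5. Discrete tests.** Exact size of the pooled chi-square test, 200 against 100:

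| Common null rate | Unrounded rule | Rounded rule |
|---|---|---|
| 10% | 0.0489 | 0.0518 |
| 20% | 0.0500 | 0.0510 |
| 30% | 0.0501 | 0.0501 |
| 40% | 0.0508 | 0.0508 |
| 50% | 0.0535 | 0.0549 |

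So 0.0505 is a nominal figure. For a discrete test the band can hold more than 0.0005 (0.0029 at a 10% rate, 0.0013 at 50%) or almost nothing.

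**6. Confidence interval.** When a test and a 95% interval use the same estimate, standard error and degrees of freedom, P > 0.05 means that the interval includes zero. A P value in the band therefore always comes with such an interval.

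**The case against.** The strongest reply is that nothing is inconsistent. The rounding sentence can be read as the operational definition of the 0.05 comparison: it states the precision at which P is judged. It is prespecified, worded alike in both documents and leaves no discretion once data are seen. Ordinary approximation error is also larger than the band, since the unrounded chi-square test already has size 0.0535 at a 50% null rate. On this view the point is a preference for unrounded P values.

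Much of that stands as an argument about importance. It does not remove the mismatch. The rounding sentence names no level other than 0.05, and the same section keeps 95% intervals, which correspond to 0.05 and not to 0.0505.

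Three narrower objections are fair:

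- SAP Sections 4.4 and 11.4 concern interim looks and treatment arms, not rounding. They show only that no other threshold is given.
- The confidence-interval argument is secure only for the continuous endpoints. For the primary endpoint, SAP Section 11.2.2.1 pools proportions and their difference but tests by logistic regression, so exact agreement is not assured under either rule.
- SAP Section 11.1 sits within the efficacy chapter, whereas Protocol Section 8.1.1 covers safety tests as well. A correction placed only in SAP 11.1 might be read as leaving the protocol's rule in force for safety.

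**Conclusion.** The concern holds and is minor. The decision rule has a nominal cutoff of 0.0505 while the plan states 0.05. The excess of 0.0005 applies to each test and does not accumulate over the fixed sequence. Sample size and estimates are unaffected, and the primary conclusion is not at realistic risk.

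The 0.0505 figure assumes a continuous P value that is uniform under the null; the realised size of discrete or imputation-based tests may differ from both 0.0500 and 0.0505. The figures for the primary endpoint assume the planned 60% and 30% responder rates and use unadjusted tests as proxies. What remains is a small, one-directional mismatch that could matter only for a borderline result, most plausibly in the ranked secondary sequence.

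**What to change.** Before unblinding for the end-of-treatment analysis, replace the rounding sentence in SAP Section 11.1 with:

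> A test is significant if the unrounded two-sided P value is less than or equal to 0.05; P values are rounded for display only. This replaces the rounding rule in Protocol Section 8.1.1, under that section's allowance for exceptions.

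Repeat the text in SAP Section 3.0 so that it clearly covers safety tests too. Because the SAP would say expressly that it replaces the protocol's rule, only one rule would be in force in the meantime.

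The cost is two sentences, stated in two places, with no change to any analysis. The protocol sentence can be aligned at the next amendment: Protocol Section 9.1 requires ethics committee approval of amendments, and this point does not justify one alone.

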The Phase 3 endometriosis clinical development program is comprised of two 6-month replicate, randomized, double-blind, placebo-controlled pivotal studies (Studies M12-665 and M12-671), each with complimentary 6-month safety/efficacy extension studies (Studies M12-667 and M12-821). The extension studies are ongoing. The primary objective of the pivotal studies are to evaluate the safety, tolerability, and efficacy, of elagolix, administered QD or BID compared to placebo, in the management of moderate to severe endometriosis-associated pain while taking into account the use of rescue analgesics. Secondary efficacy objectives include assessments of other endometriosis-related symptoms, analgesic use, as well as quality of life (QoL) endpoints. The 6-month extension studies assess the long-term safety and efficacy of elagolix for a total treatment duration of up to 12 months.

Phase 3 Clinical Development Program for Uterine Fibroids

The overall objective of the registration clinical development program is to generate requisite safety, tolerability, and efficacy data in 2 replicate 6-month Phase 3 pivotal studies and 1 safety and efficacy extension study (total 12-month treatment period) to support use of elagolix 300 mg BID with E2/NETA (estradiol 1.0 mg/norethindrone acetate 0.5 mg) for the intended indication of the chronic management of HMB associated with uterine fibroids. Furthermore, the goal is to generate data that supports long-term use with this treatment regimen.

The primary objective of these pivotal studies is to evaluate the efficacy and safety of elagolix 300 mg BID in combination with add-back therapy (E2/NETA) as compared to placebo to reduce HMB associated with uterine fibroids. Given the difficulties with extending placebo for periods beyond 6 months, the elagolix 300 mg BID alone arm serves as a reference arm, which will be useful in fully understanding the protective effects of standard dose E2/NETA on BMD over a 12-month treatment period.

Subjects who complete either pivotal study (Studies M12-815 or M12-817) will have the option to enter into the extension study (Study M12-816) to receive an additional 6 months of therapy, for a total of up to 12 months of active treatment for those randomized in the pivotal studies to active treatment and a total of 6 months of treatment for those randomized to placebo in the pivotal studies.

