4.0 Study Objective

The objectives of this study are to:

- Assess the efficacy, safety and tolerability of elagolix 300 mg BID in combination with E2/NETA (estradiol 1.0 mg/norethindrone acetate 0.5 mg QD), versus placebo to reduce HMB associated with uterine fibroids in premenopausal women 18 to 51 years of age.
- The study will also characterize the impact of E2/NETA on the safety/tolerability (including BMD and other hypoestrogenic side effects) and efficacy of elagolix.

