5.6 Discussion and Justification of Study Design

5.6.1 Discussion of Study Design and Choice of Control Groups

This Phase 3 study will be conducted as a randomized, double-blind, multi-center, placebo-controlled study in premenopausal women 18 to 51 years of age with HMB associated with uterine fibroids. The randomized, double-blind, placebo-controlled study design is the standard for unbiased assessments of treatment group differences.

This study will evaluate the safety and efficacy of elagolix 300 mg BID alone and elagolix 300 mg BID in combination with E2/NETA QD (1.0 mg/0.5 mg) versus placebo in subjects with HMB associated with uterine fibroids. The study will also assess the impact of E2/NETA on the efficacy, safety, and tolerability of elagolix, including hypoestrogenic side effects such as BMD decrease and vasomotor symptoms.

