8.1.8.4 Bone Mineral Density

The within-group percent change from baseline to Month 6 in BMD will be summarized for each treatment group with mean, standard deviation, median and two-sided 95% confidence interval. The between-group differences in percent change from baseline to Month 6 in BMD will be summarized with mean and standard error. The percent change from baseline to Month 6 in BMD will be compared between each elagolix treatment group and the placebo group as well as between the elagolix 300 mg BID group and the elagolix 300 mg BID plus E2/NETA group using ANCOVA with treatment as the main effect and baseline BMD as a covariate. Two-sided 95% confidence intervals will be constructed for the between-group differences in percent change from baseline to Month 6 in BMD.

The number and percentage of subjects with categorized percent change from baseline in BMD (e.g., $\leq -3\%$, $\leq -5\%$, or $\leq -8\%$) will be summarized for each treatment group and comparison between each elagolix treatment group and the placebo group as well as between the elagolix 300 mg BID group and the elagolix 300 mg BID plus E2/NETA group will be made.

In addition, to evaluate BMD change, the percent change from baseline to Month 6 in the Treatment Period using aggregated data from two pivotal studies (Studies M12-815 and M12-817) will be compared between each elagolix treatment group and the placebo group as well as between the elagolix 300 mg BID group and the elagolix 300 mg BID plus E2/NETA group using ANCOVA with treatment as the main effect and baseline BMD as a covariate. Two-sided 95% confidence intervals will be constructed for the differences in percent change from baseline to Month 6 in BMD.

Analysis details will be specified in the SAP.

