12.0 Safety Analysis

12.1 General Considerations

Safety analyses will be carried out using the Safety Analysis Set, which includes all subjects who received at least one dose of study drug. Safety data will be summarized by actual treatment received. If a subject receives more than one type of study drug, safety data will be analyzed in the treatment group to which she was randomized to. All safety analyses will be based on observed data. For analyses of safety endpoints, subjects who are missing an evaluation will not be included in the analysis of that particular parameter/visit, unless otherwise specified.

For continuous variables, when the analyses of change and/or percent change from Baseline to post-baseline visit(s) are performed, the within-group change from Baseline to each relevant visit will be summarized by treatment group with the mean, SD, and 95% CIs. The between-group differences will be summarized with the mean, SE, 95% CIs, and *P* value when applicable. At each post-baseline visit, the Baseline mean and post-baseline visit mean will be calculated for all subjects with baseline and post-baseline value at that visit by treatment group.

For qualitative categorical variables, Fisher's exact test will be used to analyze between-group differences when applicable. Categorical data will be summarized by number and percentage of subjects by treatment group.

Pregnancies and outcomes will also be summarized by treatment group.

Statistical comparisons will be performed between each elagolix dose group and placebo in the Treatment Period only, unless otherwise specified. There will be no testing for safety endpoints in the Post-Treatment Follow-up Period.

Information regarding corresponding statistical methods for analyses and any additional statistical measures required for a specific variable/endpoint will be specified in the relevant sections.

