12.4.1 BMD in the Treatment Period

BMD

A continuous summary of BMD at Baseline, Between Month 3 and Month 6, Month 6, and Final Visit will be provided by treatment group. This summary will include the mean, SD, median, minimum, maximum, and first and third quartiles. This analysis will be repeated excluding subjects who switched machine manufacturer type (Lunar or Hologic), subjects with scans only on Lunar machines, and subjects with scans only on Hologic machines.

The analysis of percent change in BMD from Baseline to each relevant visit in the Treatment Period will be performed. The mean percent change in BMD from baseline to Month 6 and Final Visit during the Treatment Period will be compared between each elagolix dose group and placebo, as well as between elagolix 300 mg BID group and elagolix 300 mg BID + E2/NETA group, using ANCOVA with treatment as the main effect and Baseline value of corresponding parameter as a covariate. This analysis will be repeated excluding subjects who switched machine manufacturer type (Lunar or Hologic), subjects with scans only on Lunar machines, and subjects with scans only on Hologic machines.

The number and percentage of subjects with percent change from Baseline to Between Month 3 and Month 6, Month 6, and Final Visit in the Treatment Period in mutually exclusive categories of BMD decrease: $\leq 0\%$, $> 0\% - \leq 1.5\%$, $>1.5\% - \leq 3\%$, $> 3\% - \leq 5\%$, $> 5\% - < 8\%$, and $\geq 8\%$ will be summarized by treatment group and comparison between each elagolix dose group and placebo, as well as between elagolix 300 mg BID group and elagolix 300 mg BID + E2/NETA group, will be made using Fisher's exact test.

Z-Score and T-Score

A continuous summary of the Z-score at Baseline, Between Month 3 and Month 6, Month 6, and Final Visit will be provided by treatment group. This summary will include the mean, SD, median, minimum, maximum, and first and third quartiles. A categorical summary of Z-score will be summarized at Baseline, Between Month 3 and Month 6, Month 6, and Final Visit for the following categories: ≤ -2.0 , > -2.0 to ≤ -1.5 , > -1.5 to ≤ -1.0 , and > -1.0 for all subjects, subjects with BMD decrease $\geq 3\%$ at Month 6, and subjects with BMD decrease $< 3\%$ at Month 6, respectively. The categorical summary of worst Z-score at any time in the Treatment Period will be produced by treatment group for each anatomical region.

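### Objective 2 asks what E2/NETA does to elagolix, but an estimate of elagolix plus E2/NETA versus elagolix alone is planned only for BMD

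*SAP*

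**What the plan says.** Protocol 4.0 gives the second objective as "The study will also characterize the impact of E2/NETA on the safety/tolerability (including BMD and other hypoestrogenic side effects) and efficacy of elagolix"; SAP 4.1 repeats it. Protocol 5.6.1 restates it as the "impact of E2/NETA on the efficacy, safety, and tolerability of elagolix, including hypoestrogenic side effects such as BMD decrease and vasomotor symptoms".

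For efficacy, SAP 11.1 sets the rule: "The elagolix dose groups will not be compared against each other unless otherwise specified". For safety, SAP 12.1 sets a parallel default: "Statistical comparisons will be performed between each elagolix dose group and placebo in the Treatment Period only, unless otherwise specified". For categorical safety variables the same section says that Fisher's "exact test will be used to analyze between-group differences when applicable"; that sentence names no pair of arms and sits under the versus-placebo default.

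The exception is BMD. SAP 12.4.1 compares each elagolix arm with placebo, "as well as between elagolix 300 mg BID group and elagolix 300 mg BID + E2/NETA group, using ANCOVA", and plans the same pair for the BMD-decrease categories by Fisher's exact test. Protocol 8.1.8.4 agrees ("as well as between the elagolix 300 mg BID group and the elagolix 300 mg BID plus E2/NETA group using ANCOVA") and adds the contrast in data aggregated over the two pivotal studies.

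The elagolix-alone arm is declared a reference arm (SAP 11.4). Two uses are stated. Protocol 3.2.3, under the Phase 3 program for uterine fibroids, gives BMD, "which will be useful in fully understanding the protective effects of standard dose E2/NETA on BMD over a 12-month treatment period". Protocol 8.1.7.2.8 and SAP 11.1 add that its comparison with placebo serves to check the validity of the design.

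**The concern.** The effect of E2/NETA on elagolix is the difference between the two elagolix arms. Comparing each arm with placebo answers another question. As written, the plan applies the direct contrast to one part of the objective (BMD) and excludes it by rule, or leaves it out, for the parts concerning efficacy, vasomotor symptoms and lipids.

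The protocol itself argues from this contrast. Section 3.2.2 reports that adding E2/NETA significantly lowered Phase 2b hot flush rates. Section 3.5 says that it attenuated the lipid increases seen with elagolix alone, and that benefit/risk will be defined further in this trial. Section 3.2.3 describes the impact on the bleeding endpoints as minimal, beside preliminary responder rates of 91.9% (alone) and 79% (with standard-dose E2/NETA).

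Prespecification has practical value here. Under SAP 4.4 the sponsor sees group-level results at the end-of-treatment analysis, so a contrast chosen later would be chosen with the arm results in view.

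**Working it through.** **Where the contrast is planned**

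| Outcome | Comparison in the SAP | Combination versus alone? |
|---|---|---|
| Responders (11.2.2.1) | Logistic model, each elagolix arm vs placebo, 20 imputations | No |
| MBL change to Final Month (11.3.1) | ANCOVA on imputed data, each elagolix arm vs placebo | No |
| Suppression of bleeding (11.3.2.2) | Chi-square or Fisher, each elagolix arm vs placebo | No |
| Hot flush, night sweats (12.2) | By-arm counts, severity, time to first onset | No |
| Lipids (12.3.1) | One-way ANOVA, each elagolix arm vs placebo | No |
| BMD (12.4.1) | ANCOVA and Fisher | Yes |

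A few efficacy sections (hemoglobin change, PGIC) name no pair, so the SAP 11.1 default governs them. Protocol 8.1.8.1 and 8.1.8.3 speak of treatment-group differences without naming a pair; the SAP narrows these to versus placebo.

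**The plan's own figure.** SAP 4.3 claims at least 90% power for 60% vs 30% with 200 and 100 women, two-sided alpha 0.05. The pooled rate is (100×0.30 + 200×0.60)/300 = 0.50. The null SE is sqrt(0.25×0.015) = 0.0612 and the alternative SE is sqrt(0.21/100 + 0.24/200) = 0.0574. Then z = (0.30 − 1.96×0.0612)/0.0574 = 3.13, a power of 99.9%. The claim holds as a lower bound. The sample-size section does not address combination versus alone.

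**Expected precision of the missing contrast** (200 combination, 100 alone). Half-width = 1.96 × sqrt[p_c(1−p_c)/200 + p_a(1−p_a)/100].

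| Outcome (combination vs alone) | Source of rates | Difference | Half-width | 95% CI |
|---|---|---|---|---|
| Responders 79% vs 91.9% | Preliminary Phase 2b, Protocol 3.2.3 | −12.9 points | 7.8 | −20.7 to −5.1 |
| Responders 79% vs 85% | 85% assumed | −6.0 | 9.0 | −15.0 to 3.0 |
| Responders 60% vs 72.9% | 60% from SAP 4.3; 72.9% assumed | −12.9 | 11.0 | −23.9 to −1.9 |
| Hot flush 10.8% vs 44.6% | Phase 2b Cohort 1, Protocol 3.2.2 | −33.8 | 10.7 | −44.5 to −23.1 |

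No proportion can have a half-width above 12.0 points (both rates 50%).

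Continuous outcomes: 1.96 × sqrt(1/200 + 1/100) = 0.24 SD. If 20% lack data (assumed; 160 vs 80 women), 1.96 × sqrt(1/160 + 1/80) = 0.27 SD.

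**Separate minor point.** SAP 12.3.1, 12.5 and 12.7.2 analyse change by one-way ANOVA without the baseline value. Relative to that, the ANCOVA variance is k²(1−ρ²)/(k²+1−2ρk), where k is the follow-up/baseline SD ratio and ρ the baseline–follow-up correlation. At assumed ρ = 0.3, 0.5 and 0.7, the CI width ratio is 0.806, 0.866 and 0.922 for k = 1, and 0.886, 0.945 and 0.990 for k = 1.25. That is about 1% to 19% narrower.

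**The case against.** The strongest reply is that this is a declared design choice. Both documents make combination versus placebo the comparison of interest, the alone arm is a reference, and characterizing an effect does not require a test. That stands as an argument against hypothesis tests, and none is asked for. It does not remove efficacy or vasomotor symptoms from an objective that names them, and the BMD exception shows the same contrast being used to answer that objective.

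A second reply also stands in part: much is already planned. Within-group changes carry a mean, SD and 95% CI by arm. Hot flush and night sweats are summarized by severity and onset, and hypoestrogenic events are adverse events of special interest (SAP Appendix Q). Unadjusted differences can be worked out from such tables. For responders and MBL change, if the two versus-placebo estimates come from one three-arm model, as the wording suggests, subtracting them gives a baseline-adjusted log odds ratio or mean difference. The adjusted CI would still need the covariance of the two estimates, which no described output provides.

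A reader might go further and infer that the trial could say nothing about E2/NETA outside BMD, or only something unadjusted. The planned summaries and models do not support that. Nor do the Phase 2b rates establish an efficacy loss: they are preliminary, come without n or CI, and the protocol reads them as minimal impact. They make a loss plausible enough to estimate.

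**Conclusion.** The point holds as a gap in estimation. For bleeding efficacy, hot flush, night sweats and lipids, a stated objective has no prespecified combination-versus-alone estimate with a CI. Trial size does not explain the omission: expected half-widths are about 8 to 11 points for responders, about 11 points for hot flush, and 0.24 SD for continuous outcomes. These rest on full planned arm sizes, preliminary Phase 2b rates, and the assumed rates marked above. The intervals also show a limit: an efficacy loss near 6 points would not be settled, and reporting the interval would make that plain.

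A reader might infer that the main result is weakened. It is not: the primary analysis, its power and the type I error control are untouched. The change is worth making because it lets the trial answer its own second objective at almost no cost. The ANOVA point is separate and concerns precision only.

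**What to change.** In SAP 11.1, 11.2.2, 11.3.1, 11.3.2.2, 12.2 and 12.3.1, prespecify combination minus alone with a 95% CI for:

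- (a) the responder proportion, pooled over the same 20 imputed datasets, plus the odds ratio from the same logistic model (two estimates);
- (b) change in MBL volume to Final Month, from the same ANCOVA and imputed data (one);
- (c) suppression of bleeding at Final Month, as an unadjusted difference in proportions, stating the restriction to women with at least 38 days to the Reference Day (one);
- (d) the proportions with at least one treatment-emergent hot flush and with at least one night sweat, as unadjusted differences (two);
- (e) percent change to Month 6 in LDL-C, HDL-C, triglycerides and total cholesterol, by ANCOVA with the baseline lipid value (four).

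That is 2 + 1 + 1 + 2 + 4 = 10 estimates. Name the interval method for the unadjusted proportions. Label all ten as estimation outside the fixed sequence, with no significance claims, and record them as additions to Protocol 8.1.7 and 8.1.8.

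Separately, in SAP 12.3.1, 12.5 and 12.7.2, replace one-way ANOVA on change with ANCOVA including the baseline value, recorded as a change from Protocol 8.1.8.1 and 8.1.8.3.

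The cost is SAP wording and a little programming. No new data, no added women and no alpha are needed; baseline values are already collected.
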